### **6.2 TRIAL PROCEDURES AT EACH VISIT**

#### **6.2.1 Screening**

The screening visit assessments are identical in Regimens U and M (Day -35 to Day -1)

##### **6.2.1.1 Screening Visit 1 (SV1)**

Once MTD in Regimen U will be determined, all patients will be able to enter in regimen M and therefore the patients will only performed SV2

Informed consent number 1	Written informed consent must be obtained before any study specific procedures are performed Informed consent number 1 must include consent to collection of demographic data and consent to send tumour sample from surgery to central laboratory for MGMT status assessment.
---------------------------	-----------------------------------------------------------------------------------------------------------------------------------------------------------------------------------------------------------------------------------------------------------------------------------

Demographics	sex, birth date, race
--------------	-----------------------

If proven MGMT promoter status already available prior screening as described in section 5.6.1.1, patients will not need to perform the screening visit 1.

#### 6.2.1.2 Screening Visit 2 (SV2)

Informed consent number 2 or 3*	Written informed consent number 2 must be obtained before any study specific procedures are performed. * Once the MTD in Regimen U is determined, written informed consent number 3 must be obtained before any study specific procedures are performed
In-/Exclusion criteria	Patient eligibility will be assessed
MGMT test result	Before determination of the MTD in Regimen U, the MGMT test result will decide if the patient will take part in Regimen U or Regimen M.
Cerebral MRI	Early postoperative MRI (within 72 hours after initial surgery) if available. In case a patient did not perform a Gd-enhanced MRI within 72 hours post surgery, a Gd-MRI is to be performed prior to start of study treatment.
Demographics	Sex, birth date, race (only for patients who did not need to perform Screening visit 1)
Serum $\beta$ -HCG test (Pregnancy test)	For women of childbearing potential only
Medical history	Oncological and relevant non-oncological information (section 5.3.1)
Echo or MUGA	Cardiac left ventricular function assessment Section 5.2.10)
Physical examination	Including weight and height
ECG	12-lead resting ECG will be performed
Karnofsky performance score	See Appendix 10.3
Concomitant therapy	All concomitant medications will be documented
Vital signs	Temperature, blood pressure, pulse and respiratory rate after 2 min supine rest
Safety lab parameters	Hematology (including differential), biochemistry, and urine analysis (section 5.2.6)

## 6.2.2 Treatment phases

### 6.2.2.1 Concomitant Radiotherapy treatment phase(s): Regimens U and M

#### Visit RT1 - Day 1

MMSE assessment	See Appendix 10.4
Concomitant therapy	Changes in concomitant medications will be documented
Vital signs	Temperature, blood pressure, pulse and respiratory rate after 2 min supine rest
Safety lab parameters	Hematology (including differential), biochemistry, and urine analysis (section 5.2.6)
Adverse events	Occurrence of adverse events since the last visit
Dispense study medication	BIBW 2992: supply sufficient for 30 days should be dispensed. TMZ: supply sufficient for 14 days should be dispensed (for regimen M only)
BIBW 2992 administration	For the 1 st dose, study drug should be taken under the supervision of the investigator/site staff. For timing and restrictions on food intake see Section 4.1.4
TMZ administration Regimen M only	For the 1 st dose, TMZ tablets should be taken under the supervision of the investigator/site staff. For timing and restrictions on food intake see Section 4.1.4.2
Radiotherapy	2Gy once daily (five days per week, total dose 60Gy) (See appendix 10.6)

#### Visit RT2 - Day 8

ECG	12-lead resting ECG will be performed
Concomitant therapy	Changes in concomitant medications will be documented
Vital signs	Temperature, blood pressure, pulse and respiratory rate after 2 min supine rest
Safety lab parameters	Hematology (including differential), biochemistry, and urine analysis (Section 5.2.6)
Adverse events	Occurrence of adverse events since the last visit

Compliance check	The patient should bring his/her medication and the number of remaining tablets and capsules should be counted.
BIBW 2992 administration	Just before drug administration, a PK sample should be taken. For timing and restrictions on food intake see Section 4.1.4
Blood sampling for PK	For specific time schedule refer to Section 5.5.1 and Appendix 10.1
Administration of TMZ Only for regimen M	For further information refer to Section 4.1.4.2
Radiotherapy	2Gy once daily (five days per week, total dose 60Gy) (See appendix 10.6)

## Visit RT3 - Day 15

Physical examination	including weight
Concomitant therapy	changes in concomitant medications will be documented
Vital signs	Temperature, blood pressure, pulse and respiratory rate after 2 min supine rest
Safety lab parameters	Hematology (including differential), biochemistry, and urine analysis (section 5.2.6)
Adverse events	Occurrence of adverse events since the last visit
Compliance check	The patient should bring his/her medication and the number of remaining tablets and capsules should be counted.
Blood sampling for PK	For specific time schedule refer to Section 5.5.1 and Appendix 10.1
Dispense study medication	TMZ: supply sufficient for 14 days should be dispensed (for regimen M only)
BIBW 2992 administration	Just before drug administration, a PK sample should be taken. For timing and restrictions on food intake see Section 4.1.4
Administration of TMZ Only for regimen M	For further information refer to Section 4.1.4.2
Radiotherapy	2Gy once daily (five days per week, total dose 60Gy) (See appendix 10.6)

## Visit RT4 - Day 29

Concomitant therapy	changes in concomitant medications will be documented
Vital signs	Temperature, blood pressure, pulse and respiratory rate after 2 min supine rest
Safety lab parameters	Hematology (including differential), biochemistry, and urine analysis (section 5.2.6)
Adverse events	Occurrence of adverse events since the last visit
Compliance check	The patient should bring his/her medication and the number of remaining tablets and capsules should be counted.
Blood sampling for PK	For specific time schedule refer to Section 5.5.1 and Appendix 10.1
Dispense study medication	BIBW 2992: 1 bottle should be dispensed. TMZ: supply sufficient for 14 days should be dispensed (for regimen M only)
BIBW 2992 administration	Just before drug administration, a PK sample should be taken. For timing and restrictions on food intake see Section 4.1.4.
Administration of TMZ Only for regimen M	For further information refer to Section 4.1.4.2
Radiotherapy	2Gy once daily (five days per week, total dose 60Gy) (See appendix 10.6)

## Visit RT5 - Day 42

Physical examination	Including weight
Karnofsky performance score	See Appendix 10.3
Concomitant therapy	Changes in concomitant medications will be documented
Vital signs	Temperature, blood pressure, pulse and respiratory rate after 2 min supine rest
Safety lab parameters	Hematology (including differential), biochemistry, and urine analysis (section 5.2.6)
Adverse events	Occurrence of adverse events since the last visit
Compliance check	The patient should bring his/her medication and the number of remaining tablets and capsules should be counted.
Dispense study medication	Study medication (BIBW 2992) supply sufficient for 1 month should be dispensed.

BIBW 2992 administration	For timing and restrictions on food intake see Section 4.1.4
Administration of TMZ Only for regimen M	For further information refer to Section 4.1.4.2
Radiotherapy	2Gy once daily (five days per week, total dose 60Gy) (See appendix 10.6)

## 6.2.2.2 Maintenance phase

**Regimen U**

CxV1 (day 28 +/- 3)

Visit frequency: every 4 weeks for the first 6 months after RT, every 8 weeks thereafter for the next six months and then every 12 weeks for the next year, and every 6 months (24 weeks) thereafter.

Cerebral MRI Cycle 2, 4, 6, 8, 10, 12 Cycle 15, 18, 21, 24 Cycle 30, 36 (every 6 months thereafter)	MRIs need to be prepared between day 21 and day 28 of each cycle. Tumour assessment / restaging will routinely be performed at the same time that the MRI is performed.
Physical examination	Including weight
ECG Cycle 2, 4, 6, 8, 10, 12 Cycle 15, 18, 21, 24 Cycle 30, 36 (every 6 months thereafter)	12-lead resting ECG will be performed
MMSE assessment Cycle 2, 4, 6, 8, 10, 12 Cycle 15, 18, 21, 24 Cycle 30, 36 (every 6 months thereafter)	See Appendix 10.4
Karnofsky performance score	See Appendix 10.3
Concomitant therapy	Changes in concomitant medications will be documented
Vital signs	Temperature, blood pressure, pulse and respiratory rate after 2 min supine rest
Safety lab parameters	Hematology (including differential), biochemistry, and urine analysis (section 5.2.6)

Adverse events	Occurrence of adverse events since the last visit
Compliance check	The patient should bring his/her medication and the number of remaining tablets and capsules should be counted.
BIBW 2992 administration	For timing and restrictions on food intake see Section 4.1.4
Dispense study medication	Study medication supply sufficient for 28 days should be dispensed.

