### **4.3 TREATMENT COMPLIANCE**

The study medications will be given in accordance with the protocol and under the instruction of the investigator at each visit. At all other time points, patients will take the trial drugs at home. Patients will be asked to bring the remaining trial medication at each visit to the investigator for compliance check. The remaining film-coated tablets and/or capsules will be counted by the investigator/site staff and recorded at the study site.

Discrepancies between the number of film-coated tablets and/or capsules taken and the calculated number of film-coated tablets and/or capsules the patient should have taken must be documented and explained. At the end of each treatment cycle leftover medication will be collected.

During the maintenance phase, a maximum of six consecutive doses of BIBW 2992 or seven non-consecutive doses may be missed per cycle (i.e., 28 days) for reasons other than recovery from a drug-related adverse event. These patients will be allowed to continue therapy on the trial. Patients who miss treatment medication more than that are considered non-compliant. Their treatment should be discontinued, and patients will be withdrawn from the study. Patients who discontinue or interrupt the study medication due to AE for less than 14 days are considered compliant.

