### Regimen M

Visit frequency: every 4 weeks for the first 7 months (4 weeks TMZ break followed by BIBW2992 + TMZ treatment period), every 8 weeks thereafter for the next six months and then every 12 weeks (three months) for the next year, and every 24 weeks (6 months) thereafter.

BREAK- Day 70 (day 28 +/- 3)

ECG	12-lead resting ECG will be repeated
Concomitant therapy	Changes in concomitant medications will be documented
Karnofsky performance score	See Appendix 10.3
Vital signs	Temperature, blood pressure, pulse and respiratory rate after 2 min supine rest
Safety lab parameters	Hematology (including differential), biochemistry, and urine analysis (section 5.2.6)
Adverse events	Occurrence of adverse events since the last visit
Administration of BIBW 2992	For timing and restrictions on food intake see Section 4.1.4
Compliance check	The patient should bring his/her medication and the number of remaining tablets and capsules should be counted.
Dispense study medication	Study medication supply sufficient for 28 days should be dispensed.

CxV1 (day 28 +/- 3)

Cerebral MRI Cycle 1, 3, 5, 8,10 ,12 Cycle 15, 18, 21, 24 Cycle 30, 36(every 6 months thereafter)	MRIs need to be prepared between day 21 and day 28 of each cycle Tumour assessment / restaging will routinely be performed at the same time that the MRI is performed.
Physical examination	Including weight
ECG Cycle 1, 3, 5, 8,10,12 Cycle 15, 18, 21, 24 Cycle 30, 36(every 6 months thereafter)	12-lead resting ECG will be performed
MMSE assessment Cycle 1, 3, 5, 8,10 ,12 Cycle 15, 18, 21, 24 Cycle 30, 36(every 6 months thereafter)	See Appendix 10.4
Karnofsky performance score	See Appendix 10.3
Concomitant therapy	Changes in concomitant medications will be documented
Vital signs	Temperature, blood pressure, pulse and respiratory rate after 2 min supine rest
Safety lab parameters	Hematology (including differential), biochemistry, and urine analysis (section 5.2.6)
Adverse events	Occurrence of adverse events since the last visit
Compliance check	The patient should bring his/her medication and the number of remaining tablets and capsules should be counted.
Administration of TMZ Only up to Cycle 6	For dose timing and restrictions on food intake see Section 4.1.4.2
Administration of BIBW 2992	For timing and restrictions on food intake see Section 4.1.4
Dispense study medication	Study medication supply sufficient for 28 days should be dispensed.

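### After cycle 6 the protocol's 28-day dispensing line does not match visits 8, 12 and 24 weeks apart, and the per-cycle compliance rule in Section 4.3 fits neither

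*Protocol*

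**What the plan says.** **Supply.** In Protocol Section 6.2.2.2 a single table (CxV1) per regimen lists the procedures for all maintenance visits. Both tables instruct: "Study medication supply sufficient for 28 days should be dispensed". Section 4.1.6 states that bottles hold 30 tablets.

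**Visits.** For Regimen U, Section 6.2.2.2 sets visits "every 4 weeks for the first 6 months after RT", then "every 8 weeks thereafter for the next six months and then every 12 weeks for the next year, and every 6 months (24 weeks) thereafter". For Regimen M the four-weekly period lasts seven months, because it includes the TMZ break; after that visits are "every 8 weeks thereafter for the next six months and then every 12 weeks (three months) for the next year", and 24-weekly from then on. Footnote 2 of the flow charts gives the same pattern by cycle: C8, C10, C12, then C15, C18, C21, C24, then C30, C36 and onward. No dispensing contact is scheduled between these visits.

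**Dosing.** Sections 4.1.1 and 4.1.4.1 have BIBW 2992 taken once daily without a planned gap until progression or unacceptable side effects.

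**Compliance.** In Section 4.3, for maintenance, "a maximum of six consecutive doses of BIBW 2992 or seven non-consecutive doses may be missed per cycle" (a cycle being 28 days) for reasons other than recovery from a drug-related adverse event. Then: "Patients who miss treatment medication more than that are considered non-compliant". Such patients are to stop treatment and leave the study. The same section counts tablets at visits, has leftovers collected when each cycle ends, and requires discrepancies to be documented and explained.

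**The concern.** The 28-day line fits the four-weekly period and appears to have been carried into the wider intervals unchanged. Followed as written, it leaves a patient without drug for at least half of every interval after cycle 6. Section 4.3 then counts those days as missed doses, since running out of tablets is not recovery from an adverse event.

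The patients concerned are those treated longest. At stake are long-term exposure, late safety, best response after cycle 7, and the group treated for more than a year, for whom Section 5.6 provides optional tumour analyses. If sites hand out more on their own initiative, they depart from the written instruction, while Section 8.2.1 asks for records showing that patients received what the protocol specifies.

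The second problem is measurement. Section 4.3 works per cycle, but many cycles after C6 have no visit at which tablets can be counted or leftovers collected.

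**Working it through.** **Inputs.** Supply per visit: 28 doses (6.2.2.2), or 30 if a whole bottle is given (4.1.6). One dose per day (4.1.1). Intervals of 4, 8, 12 and 24 weeks (6.2.2.2). Visit window ±3 days (6.2.2.2); footnote 2 and Section 6.1 give 2 days, so the wider window is used. Limit: six consecutive missed doses per 28-day cycle (4.3). No carry-over, because leftovers are collected (4.3).

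**Formulas.** Doses needed = 7 × weeks. Coverage = 28 / needed. Shortfall = needed − supply. The protocol states no figure to reproduce; the four-weekly row shows where the line does fit.

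| Interval | Needed | Coverage | Shortfall, 28 doses | Same, ±3 days | Shortfall, 30 tablets |
|---|---|---|---|---|---|
| 4 weeks | 28 | 100% | 0 | at most 3 | none (2 spare) |
| 8 weeks | 56 | 28/56 = 50% | 28 | 25 to 31 | 26 |
| 12 weeks | 84 | 28/84 = 33% | 56 | 53 to 59 | 54 |
| 24 weeks | 168 | 28/168 = 17% | 140 | 137 to 143 | 138 |

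After C6 each shortfall is one unbroken run. The smallest, with an early 8-week visit and a full bottle, is 53 − 30 = 23 doses against a limit of six.

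**When the gap starts.** CxV1 falls on day 28 of the cycle, so the C6 supply covers cycle 7. The first uncovered day is in cycle 8. The seventh consecutive missed dose falls on day 28 + 7 = 35 after dispensing, or 30 + 7 = 37 with a full bottle. The C8 visit is nominally on day 56, which is 56 − 37 = 19 days later, or 53 − 37 = 16 days at the early edge of the window. All seven missed doses lie within cycle 8, so the per-cycle limit is passed before the visit.

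**Does carry-over rescue it?** Suppose, contrary to Section 4.3, that the 2 spare tablets per maintenance bottle were kept. Regimen U has six such intervals before C6 and Regimen M has seven. Stock at C6 is then 6 × 2 + 30 = 42 (U) or 7 × 2 + 30 = 44 (M), still 14 or 12 short of 56. Suppose also that 18 spare tablets from the RT phase (30 + 30 − 42) were kept and were of the same strength, which is an assumption that fits only the 40 mg cohort. Stock is then 60 or 62, which covers C6 to C8 and leaves 4 or 6. The next interval has 34 or 36 tablets against 56, so it is 22 or 20 short.

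**Does supply match visits elsewhere?** Yes. BIBW 2992 for 30 days at Day 1 lasts to the next BIBW dispensing visit on Day 29, and TMZ for 14 days is given on Days 1, 15 and 29 (6.2.2.1).

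**Cycles without a visit.** C7 to C12: 6 cycles, 3 visits. C13 to C24: 12 cycles, 4 visits. C25 to C36: 12 cycles, 2 visits. So 30 − 9 = 21 of the 30 cycles have no scheduled count. A count at the next visit gives a total over two, three or six cycles. It does not show in which cycle doses were missed or whether they were consecutive.

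**The case against.** The best reply is that the line sets a supply to be given and forbids nothing more. Continuous dosing, visits scheduled to C36 and beyond, and the provisions for patients treated over a year all show that continued supply is intended. A site would probably dispense enough to reach the next visit, and few would call a shortage created by the dispensing instruction patient non-compliance. Section 6.3 also describes withdrawal from treatment as following discussion between the sponsor's monitor and the investigator. This stands as an account of likely practice. It does not remove the conflict: no section provides for a larger supply or for dispensing between visits, and the re-supply text in Section 4.1.6 concerns stock according to site needs.

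A reader might infer that everyone who passes cycle 6 must be withdrawn. The documents do not support that. A patient who stops during cycle 7 is unaffected, and withdrawal later on depends on sites applying both the dispensing line and Section 4.3 literally.

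A reader might also infer that the Section 4.3 rule cannot be applied at all after C6. That too goes further than the text, because discrepancies must be documented and explained, dispensing is part of the source data (8.2.4), and accountability records cover use by each patient (8.2.1). Even a four-weekly count cannot show whether missed doses were consecutive. What is lost after C6 is the per-cycle total, which a four-weekly count does give.

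Finally, the effect on the trial's main result is nil. DLT for the MTD is assessed during the RT period (Protocol 5.2.4; SAP 5.1). SAP violation codes C3.1 and C3.2 cover only that period, there is no per-protocol set, and compliance and exposure are described only. All of this stands.

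**Conclusion.** The dispensing line, the visit schedule and the compliance rule cannot all be followed after cycle 6. Supply falls short by 28, 56 and 140 consecutive doses (26, 54 and 138 with full bottles) against a limit of six, and the visit window does not change this. The first gap is in cycle 8. In addition, counts at visits more than one cycle apart do not by themselves supply what the per-cycle rule needs.

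This rests on one dose a day, supply as written, leftovers collected as written, and no contacts beyond the schedule. The documents do not say how many patients will reach cycle 8, and actual withdrawals depend on how sites read the text, so neither can be sized. For Regimen M the finding rests on Section 6.2.2.2 and the flow-chart notes, since the chart's grid was not available in the text reviewed. The consequence is limited to long-term exposure, late safety and best-response follow-up. It should be corrected, but it does not threaten determination of the MTD.

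**What to change.** In Section 6.2.2.2, for both regimens, reconcile the dispensing line with the visit schedule there and in flow-chart footnote 2, so that the supply handed out and the interval to the next dispensing contact match. In Section 4.3, reconcile the per-cycle missed-dose rule and the end-of-cycle collection of leftovers with visits more than one cycle apart, and say which records, besides the count, are used to judge compliance in that period. How this is done, including any change to the withdrawal rule, is for the sponsor.

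The cost is protocol wording and supply planning. If the intervals stay as they are, covering them at one tablet a day takes 56, 84 or 168 doses, which is 2, 3 or 6 bottles of 30 (60, 90 or 180 tablets), enough also for a visit 3 days late (59, 87 or 171). The downside is more drug held by patients between visits. The alternative is extra dispensing contacts.

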### Regimen M

Visit frequency: every 4 weeks for the first 7 months (4 weeks TMZ break followed by BIBW2992 + TMZ treatment period), every 8 weeks thereafter for the next six months and then every 12 weeks (three months) for the next year, and every 24 weeks (6 months) thereafter.

BREAK- Day 70 (day 28 +/- 3)

ECG	12-lead resting ECG will be repeated
Concomitant therapy	Changes in concomitant medications will be documented
Karnofsky performance score	See Appendix 10.3
Vital signs	Temperature, blood pressure, pulse and respiratory rate after 2 min supine rest
Safety lab parameters	Hematology (including differential), biochemistry, and urine analysis (section 5.2.6)
Adverse events	Occurrence of adverse events since the last visit
Administration of BIBW 2992	For timing and restrictions on food intake see Section 4.1.4
Compliance check	The patient should bring his/her medication and the number of remaining tablets and capsules should be counted.
Dispense study medication	Study medication supply sufficient for 28 days should be dispensed.

CxV1 (day 28 +/- 3)

Cerebral MRI Cycle 1, 3, 5, 8,10 ,12 Cycle 15, 18, 21, 24 Cycle 30, 36(every 6 months thereafter)	MRIs need to be prepared between day 21 and day 28 of each cycle Tumour assessment / restaging will routinely be performed at the same time that the MRI is performed.
Physical examination	Including weight
ECG Cycle 1, 3, 5, 8,10,12 Cycle 15, 18, 21, 24 Cycle 30, 36(every 6 months thereafter)	12-lead resting ECG will be performed
MMSE assessment Cycle 1, 3, 5, 8,10 ,12 Cycle 15, 18, 21, 24 Cycle 30, 36(every 6 months thereafter)	See Appendix 10.4
Karnofsky performance score	See Appendix 10.3
Concomitant therapy	Changes in concomitant medications will be documented
Vital signs	Temperature, blood pressure, pulse and respiratory rate after 2 min supine rest
Safety lab parameters	Hematology (including differential), biochemistry, and urine analysis (section 5.2.6)
Adverse events	Occurrence of adverse events since the last visit
Compliance check	The patient should bring his/her medication and the number of remaining tablets and capsules should be counted.
Administration of TMZ Only up to Cycle 6	For dose timing and restrictions on food intake see Section 4.1.4.2
Administration of BIBW 2992	For timing and restrictions on food intake see Section 4.1.4
Dispense study medication	Study medication supply sufficient for 28 days should be dispensed.

